5.5. Multiple Comparisons/Multiplicity

The test for superiority in HbA1c change from baseline (the second gated objective) will be conducted only when the test for noninferiority (the first gated objective) has been achieved. The gated objectives won't be conducted if the primary objective cannot be met.

No multiplicity test adjustment will be made for other objectives.

5.6. Patient Disposition

Patient disposition will be displayed in a flowchart showing the number of patients entered, randomized, and discontinued during the study.

Frequency counts and percentages of all randomized patients completing and discontinuing from the study will be presented for each treatment group. Reasons for discontinuation from the study and study treatment from randomization to the end of the study will be compared between treatment groups using Fisher's exact test.

Frequency counts and percentages of all patients entered and discontinued from the study prior to the lead-in period will be summarized for all entered patients. A similar summary will also be provided for the lead-in period using Enrolled Population.

A listing of the primary reason for treatment discontinuation and study discontinuation will be generated for the Randomized Population.

Patient allocation by investigator, grouped by country, will be summarized indicating the number of patients who enter the study, the number of patients who receive at least 1 dose of open-label Humalog during the lead-in period, the number of patients who are randomized to study treatment, and the number of patients who discontinue the study or study treatment during the 26-week treatment period.

A listing of the randomization treatment assignment will be generated for all randomized patients.

I8B-MC-ITSB Protocol Amendment (b) allows 1 rescreening of patients who had a screen failure or unexpectedly had to discontinue before randomization due to COVID-19 enrollment pause. A listing will be presented to show the patient's previous patient number and current patient number. Disposition tables during the lead-in phase will be further classified such that rescreening is taken into account.

5.7. Patient Characteristics

A summary table will be generated for patient baseline characteristics using all randomized patients. The variables that will be included but not limited to include the following: age, age groups (age group 1: 1 to <12, 12 to <18 years, and age group 2: 1 to <6, 6 to <12, 12 to <18 years), sex, country, ethnicity, race, height, weight, body mass index (BMI). For continuous variables, the following statistics will be provided: mean, SD, minimum, maximum, and median, and treatment groups will be compared using an analysis of variance model with a term of treatment. For categorical variables, summary statistics will include sample size, frequency and percentage, and treatment groups will be compared using Fisher's exact test or Pearson's chi-square test. A listing of patient characteristics at baseline will be provided.

A similar summary of diabetes characteristics will also be generated. The variables that will be included but not limited to include the following: duration of diabetes, the type of prandial insulin at screening, the type of basal insulin therapy at randomization, prandial insulin dosing plan (carbohydrate counting or pattern adjustment), HbA1c at screening and randomization, and HbA1c stratum.

The above summaries of baseline and diabetes characteristics will also be provided for patients who participate in the Pediatric Quality of Life addendum and complete the questionnaire both at baseline and post-baseline.

A listing of patients whose stratification factor value entered into the IWRS (for treatment group assignment) is different from the clinical database will also be provided.

For all randomized patients, the number and percentage of patients with historical conditions will be summarized by treatment group using Medical Dictionary for Regulatory Activities (MedDRA) Preferred Term (PT), and the number and percentage of patients with preexisting conditions will also be summarized by treatment group using MedDRA PT. Historical conditions are conditions that end prior to first dose of IP and pre-existing conditions are conditions that are still ongoing at first dose of IP. Events will be ordered by decreasing frequency. No statistical comparisons between treatment groups will be performed.

5.8. Treatment Compliance

The time intervals between prandial insulin dose administration time and the start time of the corresponding meal will be summarized by treatment groups based on the following categories: pre-meal dosing, >0 to ≤10 minutes, >10 to ≤20 minutes, and >20 minutes after the start of the meal for individual visits during the treatment period.

5.9. Important Protocol Deviations

Important protocol deviations (IPD) that potentially compromise the data integrity and patients' safety will be summarized by treatment group for all randomized patients. The IPDs will be identified by site monitoring and statistical programming using the clinical database. Patients with more than one IPD from the same category, subcategory, and study specific term will only be counted once per patient.

The following may significantly impact the results of the primary objective:

- lack of informed consent
- missing HbA1c at the primary endpoint

Patients with 1 or more such deviations (lack of informed consent or missing HbA1c at endpoint) will be excluded from the PP population.

The listing of important protocol deviations for all randomized patients during the entire study, with the indication of whether to be excluded from the PP population, will also be provided. The IPDs identified by site monitoring and clinical database will be integrated in the listing. If the IPD is identified by both methods, only the site monitoring IPD will be presented.

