### 7.2.1.2. Timing of Doses

Marketed insulin lispro (Humalog) will be dispensed to all patients for use throughout the lead-in period. At randomization (Visit 4), patients study treatment (LY900014 or Humalog) starting dose may be initiated unit for unit however, investigators may consider reducing the prandial or correction doses based on patient's overall glycemic status or other considerations known to investigator in order to reduce risk of postprandial hypoglycemia. In the blinded treatment groups, LY900014 and Humalog will be administered immediately prior to each meal (0 - 2 minutes). The LY900014+20 open label treatment group will administer the dose up to 20 minutes after the start of a meal.

Patients will administer IP within the time instructed by the investigator as determined by treatment randomization (blinded LY900014 or blinded Humalog; 0-2 minutes before or open-label LY900014; up to 20 minutes after the start of the meal). An occasional change in the timing of injection may be warranted due to individual circumstances and will not be considered a protocol violation unless deemed by the investigator to be excessive and noncompliant to study procedures.

The patient's basal insulin during the study can be dosed at any time and should be taken at approximately the same time each day. Patients should use the same basal insulin regimen (type and dosing frequency) throughout the study. Patients will record all insulin doses in the study diary as instructed.

Patients will be required to collect glucose values at least 4 times (before meals and bedtime) each day using the BG meter provided or a personal CGM/FGM that is approved for non-adjunctive use; i.e. results may be used to make insulin dosing decisions per their local country regulations (Section 9.1.5). The investigator will review glucose values at office and telephone visits in order to determine any insulin dose adjustments. Once BG targets are achieved and basal and prandial dose titration has been optimized, daily 4-point glucose testing frequency and timing may be adjusted at the investigator's discretion in consultation with patient and caregiver. Effort should be made to reach the BG target recommendations provided (Table ITSB.4).

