## 7.7. Concomitant Therapy

All concomitant therapies that are part of routine care are allowed and can be used during the study. Those listed in the exclusion criteria cannot be used. The subject should be encouraged to report any new concomitant medications after initiating the medication. Please check with the study team if you have any concerns or questions about a medication the subject is taking. Prohibited and restricted concomitant medications are listed below.

The following concomitant medications are NOT allowed at any time during the study

- Insulin glargine U-300, insulin degludec U-200,
- Afrezza® (inhaled insulin)
- premixed human or analog insulin
- Any noninsulin diabetes treatment therapy

The following concomitant medications ARE allowed for up to a total of 14 days during the study

- Regular human insulin, NPH or a nonstudy rapid analog insulin
- Systemic glucocorticosteroid
  - Including; intravenous, intramuscular, SC, or oral

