#### 8.1.1. Permanent Discontinuation from Study Treatment

Possible reasons leading to permanent discontinuation of IP are:

- **Subject Decision**
  - The patient/or the patient's designee, for example, parents or legal guardian requests to discontinue IP.
- The investigator may decide that the patient should stop IP. If this decision is made because of an AE, SAE, or a clinically significant laboratory value, the study drug is discontinued for that patient and appropriate measures are to be taken. Lilly or its designee is to be alerted.
- The patient becomes pregnant.
- An investigator, study site personnel performing assessments, or patient is unblinded, the patient must discontinue IP.
- The patient, for any reason, requires treatment with another therapeutic regimen or therapeutic agent that has been demonstrated to be effective for treatment of the study indication with the exception of those described in Section 7.7. Discontinuation from IP should occur prior to introduction of the new agent.
- Frequent use of prohibited concomitant medication, see Section 7.7.
- Patient has not taken IP for more than 14 consecutive days.
- Patient discontinuation is recommended by the DMC.
- **Discontinuation due to a hepatic event or liver test abnormality.** Patients who are discontinued from the IP due to a hepatic event or liver test abnormality should have additional hepatic safety data collected via case report form (CRF).

Discontinuation of the IP for abnormal liver tests **should be** considered by the investigator when a patient meets 1 of the following conditions after consultation with the Lilly-designated medical monitor:

- ALT or AST  $>8\times$ ULN
- ALT or AST  $>5\times$ ULN for more than 2 weeks
- ALT or AST  $>3\times$ ULN and total bilirubin level (TBL)  $>2\times$ ULN or international normalized ratio  $>1.5$
- ALT or AST  $>3\times$ ULN with the appearance of fatigue, nausea, vomiting, right upper quadrant pain or tenderness, fever, rash, and/or eosinophilia ( $>5\%$ )
- alkaline phosphatase (ALP)  $>3\times$ ULN
- ALP  $>2.5\times$ ULN and TBL  $>2\times$ ULN
- ALP  $>2.5\times$ ULN with the appearance of fatigue, nausea, vomiting, right quadrant pain or tenderness, fever, rash, and/or eosinophilia ( $>5\%$ )

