### 10.2. Populations for Analyses

For purposes of analysis, the following populations are defined:

Population	Description
Entered	All patients who give informed consent.
Randomized	All patients who are randomly assigned to study treatment at Visit 4. Treatment group will be defined on the basis of the treatment the patients are assigned.
Safety	All randomized patients who receive at least 1 dose of the randomly assigned investigational product (IP). Treatment group will be defined on the basis of the treatment the patients are assigned.
Completer	Patients included in the randomized population who have completed Week 26 of study treatment without permanent discontinuation of IP. Treatment group will be defined on the basis of the treatment the patients are assigned.
Per Protocol	Patients included in the randomized population who have completed Week 26 of study treatment without permanent discontinuation of IP and without significant protocol deviations through Week 26 that would significantly impact the primary objective. Treatment group will be defined on the basis of the treatment the patients actually receive.

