5.11. Efficacy Analyses

5.11.1. Primary Outcome and Methodology

The primary objective of this study is to test the hypothesis that LY900014 is noninferior to Humalog on glycemic control (noninferiority margin [NIM]=0.4% for HbA1c) in patients 1 to <18 years of age with T1D, when administered as prandial insulin, in combination with basal insulin for 26 weeks. There will be 2 primary analysis methods, each tested at the full significance level of 0.05.

For the US FDA submission (using the ITT estimand), all randomized subjects, regardless of their postbaseline result availability, will be included in the analysis. Due to COVID-19, patients are allowed to have their laboratory data collected at a local laboratory if there is any ongoing extenuating situation, such as travel restriction. HbA1c data collected from the local laboratory will be included in the analysis in the same way as those collected from the central laboratory. The missing endpoints will be imputed by the copy reference or the return to baseline approach. For the copy reference approach, the reference for each treatment group is from the retrieved dropout patients who discontinue IP but have the measurement at the primary endpoint in the same treatment group. If there are only a limited number of patients in the reference group that leads to a failure in performing the proposed multiple imputation analysis such that the model cannot converge, or the number of records in the reference group is less than the number of records with missing data, the missing endpoints will be imputed by the return to baseline

approach. For the return to baseline approach, the patient-level observed baseline value plus a noise will be used to impute the missing endpoints. The noise follows a normal distribution with the variability estimated from the “washout HbA1c data.” The “washout HbA1c data” will be derived by subtracting the corresponding treatment mean at Week 26 from individual non-missing HbA1c values at Week 26. After imputation, the primary efficacy comparison will be based on the contrast between LY900014 and Humalog from an ANCOVA. The model for the change from baseline to the Week 26 HbA1c endpoint will include treatment and strata (pooled country, type of basal insulin, and age group) as fixed effects and baseline HbA1c as a covariate. The final estimates will be the combined estimates from at least 1000 imputations.

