For non-FDA submissions, the primary efficacy comparison will be based on the contrast between LY900014 and Humalog at Week 26 (Visit 15) from the MMRM analysis of change from baseline in HbA1c including data collected from all randomized patients prior to permanent discontinuation of IP through Week 26 (efficacy estimand). In contrast to the population of ITT estimand, randomized patients with a baseline and at least one postbaseline result will be included in the analysis. The model for the analysis of the primary efficacy endpoint of change from baseline in HbA1c will include the fixed class effects of treatment, strata (pooled country, type of basal insulin, and age group), visit, and treatment-by-visit interaction, as well as the continuous, fixed covariates of baseline value. An unstructured covariance structure will be used to model the within-patient errors. Significance tests will be based on LS means and Type III tests. If this analysis fails to converge, the following covariance structures will be tested in order:

- Toeplitz with heterogeneity
- autoregressive with heterogeneity
- compound symmetry with heterogeneous variances
- Toeplitz
- autoregressive
- compound symmetry without heterogeneous variances

The first covariance structure that converges will be used. The Kenward-Roger approximation will be used to estimate denominator degrees of freedom.

For both primary analysis approaches, LY900014 will be declared noninferior to Humalog if the upper limit of the 2-sided 95% CI for the LS mean difference in the change from baseline in HbA1c for LY900014 minus Humalog is below +0.4%. In addition, the 95% CI for the treatment difference will be compared to an alternative NIM of +0.3%. Both estimands will be tested at the full significance level of 0.05.

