5.11.2. Additional Analyses of the Primary Outcome

The primary MMRM analysis model will be repeated using the PP and Completer populations as a sensitivity analysis. If the conclusion differs from that of all randomized patients, the data and analyses will be further investigated.

A secondary analysis model for the efficacy estimand will be an ANCOVA for HbA1c change from baseline to the study primary endpoint, using the model with strata (pooled country, type of basal insulin, and age group) and treatment as fixed effects and baseline as a covariate. Missing endpoints will be imputed using the LOCF approach using postbaseline data only.

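### SAP 5.9 allows only two Per-Protocol exclusions, so PP is nearly the Completer set and neither sensitivity analysis tests noninferiority against treatment deviations in patients who stayed on IP

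*SAP*

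**What the plan says.** Protocol 10.2 and the population table in SAP 5.1 build PP in two steps. The patient must have completed Week 26 of treatment without permanently discontinuing IP, which is also the whole Completer definition. The patient must also be "without significant protocol deviations through Week 26 that would significantly impact the primary objective". PP groups patients by treatment actually received, Completer by treatment assigned.

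SAP 5.9 names what counts as such a deviation: lack of informed consent, and no HbA1c at the primary endpoint. It then states the rule: "Patients with 1 or more such deviations (lack of informed consent or missing HbA1c at endpoint) will be excluded from the PP population". Other important deviations are summarized and listed with a flag for PP exclusion, but no rule makes them exclusionary.

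The use of the set is in SAP 5.11.2: "The primary MMRM analysis model will be repeated using the PP and Completer populations as a sensitivity analysis".

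The protocol does set treatment rules that a completer can break. For some therapies, 7.7 says "The following concomitant medications are NOT allowed at any time during the study". It caps regular, NPH or non-study rapid-acting insulin, and systemic glucocorticosteroids, at 14 days in total. Under 7.2.1.2 an occasional change in injection timing "will not be considered a protocol violation unless deemed by the investigator to be excessive and noncompliant to study procedures".

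**The concern.** A per-protocol analysis beside a noninferiority test is normally there to ask whether the conclusion holds in patients treated as planned. Here a completer who used a barred diabetes therapy, exceeded the 14-day allowance, or habitually injected outside the assigned window stays in PP as long as consent and a Week 26 HbA1c exist.

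Timing matters particularly. Apart from open-label status, it is what separates LY900014+20 from mealtime LY900014, and the survey cited in Protocol 3.2 shows habits ranging from 15 minutes before the meal to after its start.

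What is at stake is interpretation. Agreement between the PP and Completer results is almost built in, and could be reported as robustness to nonadherence when nonadherence was not examined.

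**Working it through.** **Comparing the two sets**

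- Completer: randomized, finished Week 26, no permanent IP discontinuation; grouped as assigned.
- PP: the same, minus patients without consent, minus patients without a Week 26 HbA1c; grouped as received.

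The two MMRM runs can therefore differ only through (i) completers without valid consent, (ii) completers with no Week 26 value, who contribute only Visits 7 and 10 to the Completer run, and (iii) anyone who received a treatment other than the one assigned.

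**Does another planned analysis fill the gap?**

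- Efficacy estimand: drops data only after permanent IP discontinuation.
- ITT estimand: keeps all data regardless of IP use.
- Tipping-point, LOCF and COVID-19 analyses: concern missing values.
- SAP 5.8: summarizes dose-to-meal intervals by arm, with all pre-meal dosing in one category.
- SAP 5.10: compares concomitant medication between arms, without linking it to HbA1c.

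None re-estimates the HbA1c contrast without patients who had treatment deviations.

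**The plan's own figures**

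Inputs from Protocol 10.1: SD 1.1; 240, 240 and 120 completers; margin 0.4 (alternative 0.3); assumed difference 0 (0.07 for LY900014+20); 15% dropout. From SAP 5.11.1: "There will be 2 primary analysis methods, each tested at the full significance level of 0.05".

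Power = Φ((margin − difference)/SE − 1.96), with SE = 1.1 × √(1/n₁ + 1/n₂).

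- LY900014 vs Humalog: SE = 1.1 × √(2/240) = 0.1004. Power is 97.8% at margin 0.4 and 84.8% at 0.3 (stated: above 95% and above 80%).
- LY900014+20 vs Humalog: SE = 1.1 × √(1/240 + 1/120) = 0.1230. Power = Φ(0.33/0.1230 − 1.96) = 76.5% (stated: about 76%).
- 240/0.85 rounds up to 283 and 120/0.85 to 142; 2 × 283 + 142 = 708, as stated.

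These reproduce and do not depend on how PP is defined.

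**What a stricter PP set would cost in precision**

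The documents give no deviation rate, so the excluded share is assumed, and equal across arms. Half-width = 1.96 × SE. Power is at margin 0.4 under the plan's assumed differences.

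| Share excluded | n per blinded arm / n in +20 | Half-width, LY900014 vs Humalog | Power | Half-width, +20 vs Humalog | Power |
|---|---|---|---|---|---|
| 0% | 240 / 120 | 0.20 | 97.8% | 0.24 | 76.5% |
| 10% | 216 / 108 | 0.21 | 96.6% | 0.25 | 72.1% |
| 20% | 192 / 96 | 0.22 | 94.6% | 0.27 | 67.0% |
| 30% | 168 / 84 | 0.24 | 91.5% | 0.29 | 61.2% |

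This is a two-sample approximation to the MMRM.

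**The case against.** The strongest reply is that PP does remove some serious treatment deviations, through the Completer condition. Protocol 8.1.1 lists, among reasons for permanent discontinuation, "Frequent use of prohibited concomitant medication, see Section 7.7", more than 14 consecutive days off IP, and unblinding; 7.6 adds consistent noncompliance. This stands in part. But 8.1.1 lists possible reasons, 7.6 says such patients may be discontinued, and the condition is shared with the Completer set, so it does nothing to separate the two analyses.

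Second, the decision does not rest on PP. Under SAP 5.11.1, "LY900014 will be declared noninferior to Humalog if the upper limit of the 2-sided 95% CI for the LS mean difference" falls below +0.4%, and that is judged on the two primary estimands. This stands and limits the weight of the point.

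Third, excluding patients on post-randomization behavior breaks the randomized comparison, and timing is poorly sampled: Protocol 9.1.5 asks for dose times on at least 3 days before each visit. Both stand as limits on any fix.

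A reader might go further than the documents allow in four ways:

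- That PP cannot check the noninferiority result at all. It still addresses IP discontinuation and missing endpoints.
- That the trial's false-noninferiority rate is inflated by a calculable amount. This needs a deviation rate the documents lack, and deviators who behave like the comparator. A mistimed LY900014 patient still receives LY900014. Protocol 3.2 says current rapid-acting analogues are ideally injected 10 to 15 minutes before eating, so early Humalog dosing could work against noninferiority. A different PP rule would also leave the primary error rate unchanged.
- That wrong-IP patients need an exclusion. Grouping by treatment received already handles them.
- That any basal switch must exclude. Protocol 5.1 asks only that switching brands be avoided when possible.

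**Conclusion.** The point holds as a defect in a supportive analysis. SAP 5.9 states a closed rule that empties the second half of the PP definition, so the PP run adds little to the Completer run, and no planned analysis tests the noninferiority conclusion against treatment deviations among patients who stayed on IP. This follows from the definitions and needs no numerical assumption.

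The effect on the HbA1c difference cannot be sized, and its direction is open. The primary analyses, the noninferiority decision and the sample size are untouched. The change is worth making because it is cheap and because PP/Completer agreement would otherwise be easy to over-read.

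**What to change.** Before unblinding, add to the PP exclusions in SAP 5.9:

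1. use of a therapy listed as not allowed in Protocol 7.7;
2. non-study insulin or systemic glucocorticoid beyond the 14-day total in 7.7;
3. injection timing outside the assigned window in more than a prespecified share of recorded doses.

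Apply item 3 by the same data-driven rule in every arm, not by investigator judgement, because LY900014+20 is open-label. The share, and any tolerance around the window, is for the sponsor to fix while blinded. These rules define an analysis set only and do not alter how patients are managed. Report PP for both noninferiority contrasts, as supportive, with the number excluded by arm and reason.

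The cost is SAP wording and programming on planned diary, concomitant-medication and deviation data. Timing needs a new derivation, because SAP 5.8 does not separate 0 to 2 minutes before the meal from earlier injection. The downsides are a smaller set with a wider interval (see the table), possible selection from post-randomization exclusions, and timing known only for the sampled diary days. The assigned windows also differ in width, 2 minutes against 20, so even a uniform rule may exclude unevenly; reporting by arm would show this.

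If the sponsor keeps the two-item list, the SAP should justify it and not present agreement between PP and Completer results as evidence of robustness to nonadherence.
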